MedDRA	Medical Dictionary for Regulatory Activities
MMRM	mixed model for repeated measurements
PCS	potentially clinically significant
PYE	patient years of exposure
SAE	serious adverse event
SAS [®]	statistical software package from the SAS [®] Institute
SOC	system organ class
TEAE	treatment-emergent adverse event
WHO-DD	World Health Organization Drug Dictionary

1 Objectives

1.1 Primary Objective

- To evaluate the safety and tolerability of the long-term treatment with Lu AF35700

1.2 Exploratory Objective(s)

[figure not shown]
- to evaluate the long-term safety and tolerability of daily and weekly doses of Lu AF35700 in patients with schizophrenia during the 52-week treatment period
- to evaluate the therapeutic effect of daily and weekly doses of Lu AF35700 in patients with schizophrenia over a period of 52 weeks on:
 - psychotic symptoms
 - negative symptoms
 - global clinical impression
 - remission rate
 - quality of life and functioning
 - treatment satisfaction
 - resource utilisation

2 Study Design

- This study was a multi-national, multi-site, open-label, flexible-dose, long-term (52-week) safety study in patients with schizophrenia who had participated and completed a study investigating Lu AF35700 including studies 16159A and 16323A.
- Originally, it was planned to also include patients, who had not previously participated in a study investigating Lu AF35700. However, this was never implemented due to a very high roll-over rate from study 16159A.
- The adjustment of Lu AF35700 dosing regimen (10 mg/day or 20 mg/day) during the course of the study was left to the investigator's clinical judgement.
- For patients who had completed the study 16159A, the daily dosing regimen (10 mg/day or 20 mg/day) could be switched to weekly dosing regimen (70 mg/week) according to the investigator's clinical judgement. The number of patients under weekly dosing regimen was limited to 50 patients by IVRS/IWRS.

An overview of the study is presented in [Panel 1](#).

Panel 1 Study Design

All patients, including patients who withdraw, are scheduled for a Safety Follow-Up Visit 42 days after last dose of IMP. The follow-up includes collection of data to address the primary endpoint in a limited sense, i.e. AEs are collected if they are on-going at the Primary Outcome/Withdrawal Visit or if new SAEs have occurred. Laboratory tests are taken if these were clinically significantly abnormal at the Primary Outcome/Withdrawal Visit.

3 Definitions

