- The Safety Follow-up Visit will be done 6 weeks (+3 days) after the last dose of IMP. This visit can be a telephone contact, unless an SAE has occurred since last visit or unless there was a clinically significant abnormal safety laboratory test value at the last visit. In such cases, safety follow-up(s) must be scheduled to allow for a medical examination and/or blood sampling. Further Safety Follow-up Visits beyond 6 weeks may be needed as judged by the

- investigator (if further Safety Follow-up Visits are performed, these must be recorded in the patient's medical record, and not in the CRF).
- e. If the date of a patient visit does not conform to the study plan, subsequent visits should be planned to maintain the visit schedule relative to the Baseline Visit. The number of days between 2 visits should not exceed the number of days for which the patient has been dispensed IMP.
  - f. For *16159A-patients* and *16323A-patients*, the data will be linked respectively from the Screening Visit in the study 16159A eCRF or from the Screening Visit in the study 16323A eCRF, when applicable.
  - g. For *16159A-patients* and *16323A-patients*, results from effectiveness/safety assessments and blood/urine samples performed respectively at the Primary Outcome Visit (Visit 12) in study 16159A or at the last day of the dosing period (Day 42) in study 16323A (when available) will be linked to the Baseline Visit (Visit 1) in study 16159B, when applicable.
  - h. For *16159A-patients*, HEA data will be linked from the Baseline A Visit in the study 16159A eCRF.
  - i. To be performed only for newly recruited patients not previously participating in a study investigating Lu F35700.
  - j. Exploratory gene expression profiling (RNA) and metabolomics/proteomics are covered by the main Patient Information Sheet.
  - k. Sampling for pharmacogenetics is optional and a separate Patient Information Sheet covers this analysis. This sampling should preferably be at the Baseline Visit, but may be collected at any visit that includes a clinical safety laboratory sample.
  - l. For *16159A-patients* and *16323A-patients*, ongoing adverse events from study 16159A and 16323A, respectively, are to be transferred by the investigator to the eCRF, when applicable.
  - m. Only for adverse events ongoing at the Primary Outcome/Withdrawal Visit and new SAEs.
  - n. Only to be taken if the laboratory test was clinically significantly abnormal at the Primary Outcome/Withdrawal Visit.

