### 1.1.5.2 Pharmacokinetics

A preliminary integrated popPK analysis was performed on data from studies 14198A, 14754A, 15867A, and 15868A.

In the popPK model, the absorption phase was adequately described by first-order absorption (absorption rate constant  $[k_a] = 0.27$  L/h) with lag-time (1 h). The distribution profiles of both Lu AF35700 and Lu AF36152 were best described by two-compartment models with central and peripheral compartments. The population volume of distribution of Lu AF35700 and Lu AF36152 was estimated to 5442 and 4933 L, respectively. Plasma protein binding was investigated *in vitro* in human plasma and, overall, Lu AF35700 was classified as “highly” protein bound (95% to 99%). The apparent oral clearance of Lu AF35700 and Lu AF36152 was estimated to 29 L/h and 15 L/h, respectively. From the population estimates, the elimination half-life for Lu AF35700 and Lu AF36152 was estimated to 143 hours and 250 hours, respectively.

Preliminary results from the MAD study indicate that for the patients receiving therapeutically relevant doses of Lu AF35700, the parent compound at Day 21/24 had a median  $t_{max}$  of 8 hours, mean  $C_{max}$  ranging from 24.6 to 43.8 ng/mL, and mean area under the curve from zero to 24 hours ( $AUC_{0-24h}$ ) ranging from 455 to 759 ng·h/mL. For the major metabolite Lu AF36152, the corresponding values were a median  $t_{max}$  ranging from 9 to 14 hours, mean  $C_{max}$  ranging from 25.2 to 43.8 ng/mL, and mean  $AUC_{0-24h}$  ranging from 475 to 685 ng·h/mL.

Please refer to the *Investigator’s Brochure* for a summary of PK parameters.

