In the MAD study, in the cohorts with the daily dosing regimen, an increase in creatine phosphokinase (CPK) value was observed in the Follow-up Period on assessment days immediately after the termination of Lu AF35700 treatment or one week thereafter. The increase occurred in all Lu AF35700 dosing groups and was greatest (descending order) in the cohorts where patients received 20, 5, and 16 mg/day. The median CPK values were within the reference range (for men: 60 to 400 IU/L) and never >320 IU/L. The cohort in which women were treated with Lu AF35700 showed no increase in CPK values during the treatment period. The fractionated CPK analysis showed that the post-treatment increased CPK values were derived from muscle tissue. In the cohorts with the once-weekly dosing regimen, there were no apparent treatment or dose-related trends in mean or individual CPK values. There were no apparent treatment or dose-related trends in mean or individual data for any of the other clinical laboratory parameters.

In the MAD study, the safety and tolerability was not influenced by the formulation (oral solution *versus* tablet) or the sex of the patient.

The total number of healthy subjects (74) who have received Lu AF35700 is lower than that for patients (84) and they have generally been exposed to lower doses of Lu AF35700 for shorter duration. However, the most frequently reported adverse events in healthy subjects (somnolence, fatigue, headache, and dizziness) were similar to those in patients.

Based on safety and tolerability data from the single-dose PET and AME studies (studies 15867A and 15868A) and the FIH study in healthy subjects (study 14198A), and the MAD study in patients with schizophrenia (study 14754A), a single dose of up to 30 mg Lu AF35700 and multiple doses in the dose range 5 to 30 mg/day or 45 or 75 mg once weekly for 21 days, are safe and well tolerated.

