### **8.5 Safety Follow-up Visit/Contact (Visit 18)**

The safety follow-up is conducted to capture serious adverse events (SAEs) that occur during the Safety Follow-up Period as well as to follow up on the outcome of adverse events ongoing at the end of the Treatment Period. The safety follow-up must be conducted 42 days (+3 days) after the last dose of IMP. The safety follow-up may either be conducted as a visit to the site or as a telephone contact.

If any new SAEs have occurred since the last assessment at which the patient received IMP, the safety follow-up must, when possible, be a visit to the site.

For adverse events that were ongoing at the end of the Treatment Period and that resolved during the Safety Follow-up Period, the stop date must be recorded. For non-serious adverse events still ongoing at the safety follow-up, the stop date must be recorded as "ongoing". SAEs must be followed until resolution or the outcome is known.

Patients with a clinical safety laboratory test value that was out-of-range at the Primary Outcome or Withdrawal Visit and judged clinically significant must be followed according to accepted medical standards for up to 42 days or until the value normalises or stabilises or a diagnosis or a reasonable explanation has been established. For these patients, safety follow-up visits must be scheduled to allow for a medical examination and/or blood sampling. The investigator must decide whether further safety follow-up visits are required after 42 days. If further safety follow-up visits are made, these must be documented in the patient's medical record and not in the eCRF.

Patients who withdrew due to elevated AST or ALT values (see section 5.4) should be followed until the values normalise or stabilise or a diagnosis or a reasonable explanation has been established (see section 10.5).

The safety follow-up for patients who withdraw consent must be performed, if at all possible; any information collected will be recorded in the patients' medical records.

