#### **10.5 Treatment and Follow-up of Adverse Events**

Patients with adverse events must be treated in accordance with usual clinical practice at the discretion of the investigator.

Non-serious adverse events must be followed up until resolution or the safety follow-up assessment, whichever comes first. At the safety follow-up, information on new SAEs, if any, and stop dates for previously reported adverse events must be recorded.

It is the responsibility of the investigator to follow up on all SAEs until the patient has recovered, stabilised, or recovered with sequelae, and to report to Lundbeck all relevant new information using the same procedures and timelines as those for the initial report. Relevant information includes discharge summaries, autopsy reports, and medical consultations.

SAEs that are spontaneously reported by a patient to the investigator after the safety follow-up assessment must be handled in the same manner as SAEs that occur during the study. These SAEs will be captured in the PV database.

Patients with clinically significant out-of-range clinical safety laboratory test values at the Primary Outcome or Withdrawal Visit must be followed in accordance with usual clinical practice and be scheduled for a Safety Follow-up Visit to allow for a medical examination and/or blood sampling (see section 8.5).

Patients who withdraw due to elevated AST or ALT values (see section 5.4) must be followed until the values normalise or stabilise or a diagnosis or a reasonable explanation has been established. Additional medical examinations (for example, ultrasound scanning and/or sampling for serology, conjugated bilirubin, INR) should be considered. A gastroenterology or hepatology consultation should also be considered.

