12.1 Adverse Events

12.1.1 General Methodology for Adverse Events

Unless otherwise specified, tables, and graphs will be based on the APTS. Listings will be based on the APES.

All the tables will be presented for the total group. Three tables will be split by previous treatment as well, see section [12.1.6](#) and [12.1.9](#).

Unless otherwise specified, the summaries of adverse events will include the number and percentage of patients with an adverse event.

Only stop-dates for ongoing events at the Primary Outcome/Withdrawal Visit, and new SAEs are collected in the Follow-up Period. Therefore, adverse events in the Follow-up Period will be included in the summaries for the Treatment Period (periods are defined in section [12.1.3](#)).

Listings of adverse events will be sorted by site, previous treatment group, patient screening number (from the extension study), and adverse event start date, and include preferred term, investigator term, adverse event start date, days since first dose of IMP, duration of the adverse event, date of death, action taken, causality, intensity, seriousness, and outcome. For adverse events that change in intensity/seriousness, each intensity/seriousness will be

included. Imputed adverse event start dates (see section 19.3.5) will be included in the listings, where information about the imputation will be included as a flag in the end of the date (M = month and day imputed or D = day imputed).

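### New non-serious adverse events starting between the last visit and the 42-day contact are not recorded, although exposure is still substantial for about two to three weeks after the last dose

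*SAP*

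**What the plan says.** Protocol and SAP state one rule, several times and consistently.

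- **SAP Section 2**, below the design panel: "The follow-up includes collection of data to address the primary endpoint in a limited sense", that is, "AEs are collected if they are on-going at the Primary Outcome/Withdrawal Visit or if new SAEs have occurred".
- **SAP 12.1.1**: "Only stop-dates for ongoing events at the Primary Outcome/Withdrawal Visit, and new SAEs are collected in the Follow-up Period". For that reason, follow-up events are folded into the Treatment Period summaries.
- **Protocol Panel 2, footnote m** (repeated in SAP Appendix IV), on adverse events at Visit 18: "Only for adverse events ongoing at the Primary Outcome/Withdrawal Visit and new SAEs".
- **Protocol 10.5**: "At the safety follow-up, information on new SAEs, if any, and stop dates for previously reported adverse events must be recorded".
- **Protocol 8.5**: "The safety follow-up must be conducted 42 days (+3 days) after the last dose of IMP". Every patient is due this contact, in person or by telephone.

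Around this rule stand four further definitions. Adverse events are the first-listed primary endpoint (protocol 16.1, SAP 4.1). A treatment-emergent event is defined by onset or worsening from the first dose onward, with no closing date (SAP 12.1.2). SAP 12.1.4 defines a separate category for events starting after the last Treatment Period visit. Exposure and patient-years of exposure (PYE) end at the last dose (SAP 10), and PYE is shown in the adverse-event overview (SAP 12.1.5).

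Protocol 1.1.5.2 gives elimination half-lives of parent and metabolite as "143 hours and 250 hours, respectively". Protocol 1.1.2 describes the metabolite as pharmacologically similar to the parent but less potent in vivo.

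**The concern.** A non-serious event that begins the day after the last visit has no route into the database, yet the drug is cleared slowly. Events under residual exposure, and non-serious events on stopping, would be missing from the main endpoint of a long-term safety study. The contact at which they could be asked about already takes place.

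The tables have a second problem. Serious events are ascertained up to the follow-up contact, non-serious events only up to the last visit, and SAP 12.1.1 puts both into the same Treatment Period summaries. Two observation windows are mixed in one table, and the PYE beside the counts covers neither post-dose window.

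**Working it through.** **Inputs.** Half-lives 143 h and 250 h (protocol 1.1.5.2); follow-up at 42 days = 1008 h (protocol 8.5); more than 500 patients (SAP 16). The plan has no sample-size or power figure that bears on this point.

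**Check of the half-lives.** With the stated volumes (5442 and 4933 L) and apparent clearances (29 and 15 L/h), ln 2 × V/CL gives 0.693 × 5442/29 = 130 h and 0.693 × 4933/15 = 228 h, about 9% below the stated values. This is not an error: the model has two compartments, and the inter-compartmental clearance needed for the terminal half-life is not given. The stated values are used.

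**Share of the end-of-dosing level remaining**, by 2^(−24d/t½) after d days. For the metabolite, a second column allows for continued formation from parent. It assumes a parent-to-metabolite chain at steady state: (kp·e^(−km·t) − km·e^(−kp·t))/(kp − km), with kp = ln 2/143 and km = ln 2/250 per hour.

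| Day after last dose | Parent | Metabolite, simple decay | Metabolite, chain |
|---|---|---|---|
| 7 | 44% | 63% | 87% |
| 14 | 20% | 39% | 66% |
| 21 | 9% | 25% | 46% |
| 28 | 4% | 16% | 31% |
| 42 | 0.8% | 6% | 13% |

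Example: parent at day 7 is 2^(−168/143) = 0.443. The 42 days are 1008/143 = 7.0 parent and 1008/250 = 4.0 metabolite half-lives. With the shorter values of 130 and 228 h, days 7 and 14 become 41% and 17% for parent and 60% and 36% for metabolite, so the picture does not depend on which pair is used.

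**Length of the gap.** For a patient whose last visit coincides with the last dose, it is 42 days, or 42/364 = 11.5% of the planned treatment time. For 500 such patients that is 500 × 42/365.25, or about 57 patient-years. It is shorter for anyone seen some days after the last dose.

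**Number of events missed.** The documents give no rate of non-serious events after stopping. Purely as an assumption, if 1%, 5% or 10% of 500 patients had one in the gap, 5, 25 or 50 patients would be affected. Nothing in the documents favours any of these values.

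**What each rule lets through.**

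| Event | Recorded? |
|---|---|
| Any event up to the Primary Outcome or Withdrawal Visit | Yes |
| Event ongoing at that visit | Yes, with stop date |
| New serious event before the contact | Yes, and summarised |
| Laboratory value clinically significant at the last visit | Yes, followed up (protocol 8.5, 9.5.2) |
| New non-serious event after that visit | No |

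Only the last row is lost. The follow-up category in SAP 12.1.4 can therefore receive new events only if they are serious.

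**The case against.** The strongest reply is that this is a deliberate and disclosed choice. The rule is uniform across both documents, the SAP admits the limitation, the primary objective concerns long-term treatment, and an exploratory objective is confined to the 52 weeks. That stands as far as it goes: there is no contradiction to resolve. A treatment-emergent definition without an end date lets follow-up serious events count and does not promise full capture off drug. But neither document gives a reason for leaving out the non-serious events.

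Three stronger readings are tempting and not supported.

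- *Late and withdrawal-emergent events are missed in general.* They are not. New serious events are collected and summarised, and ongoing events are followed.
- *Six weeks are unobserved for every patient, and early withdrawals are worst hit.* The 42 days run from the last dose, and the Withdrawal Visit, with full adverse-event assessment, comes as soon as possible after the patient stops. Events before that visit are recorded.
- *The earlier multiple-dose study already showed what would be lost.* It reported a CPK rise "observed in the Follow-up Period on assessment days immediately after the termination of Lu AF35700 treatment" or a week later (protocol 1.1.5.3). That is a laboratory change with medians inside the reference range and no apparent trend under weekly dosing. An adverse-event question would not detect it, and the documents report no clinical event emerging on withdrawal.

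It is also fair that residual drug is not a count of missed events, that little remains by day 42, and that patients return to usual care after the study. Another antipsychotic may then be started and blur attribution. These points limit the value of the extra data and argue for showing them separately; they do not argue for not asking.

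**Conclusion.** The point holds for new non-serious adverse events with onset between the last visit and the 42-day contact. For about the first two to three weeks after the last dose exposure is substantial: parent 44% and metabolite 63% at day 7, then 20% and 39% at day 14. By day 42 it is about 1% and 6%, or 13% for the metabolite if continued formation is allowed for. These figures rest on the protocol's preliminary population estimates and on decay at the terminal half-life from the last dose. A faster early distribution phase would lower them, and continued formation raises the metabolite figures.

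The effect on the primary endpoint is under-ascertainment of unknown size, and the documents do not support a claim that it is large. Separately, and whatever its size, merging follow-up serious events with Treatment Period events while PYE stops at the last dose leaves numerator and exposure on different time bases. The change is worth making because it is cheap; the omission does not invalidate the safety evaluation.

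**What to change.** **If follow-up contacts are still to come.** At Visit 18, ask the open adverse-event question that protocol 9.5.1 already prescribes for visits, and record every new event, serious or not. Align protocol Panel 2 footnote m, 8.5 and 10.5, and SAP Section 2, 12.1.1 and Appendix IV. The SAP alone cannot bring this about; it needs the protocol and the eCRF.

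**In the SAP in either case.** Tabulate events with onset in the Safety Follow-up Period, as already defined in SAP 12.1.4, in their own table by preferred term, and keep them out of the Treatment Period summaries. The listings already carry start dates, so no new derivation is needed.

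**If collection has ended**, as the past-tense design description and the enrolment of more than 500 patients suggest it may have. Tabulate the follow-up serious events separately and state in the report that non-serious events starting after the last visit were not ascertained.

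**Cost.** Text changes in the places named, some data entry and one further table; no extra visit or sample. Two downsides remain: recall over 42 days, often by telephone, is imperfect, and antipsychotic treatment started after the study will confound some of the events recorded.

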3.1 Definition of Baseline

The baseline value is the value captured at the Baseline Visit of study 16159B. For efficacy/safety assessments and blood/urine samples this will be the value captured at the Primary Outcome Visit of study 16159A or at the last day of the dosing period (Day 42) in study 16323A.

For baseline characteristics captured at screening of the lead-in study, the baseline value in this study is the one captured either at the screening or baseline visit of the lead-in-study,

whichever is later. An exception to this is blood sampling for CYP2D6 and CYP2C19 genotyping, which is performed at randomization for 16159A patients.

3.2 Definition of Periods

The total study duration per patient from baseline to safety follow-up will be up to 58 weeks.

The study will consist of 2 periods:

- Treatment period – 52 weeks
- Safety follow up period – 6 weeks

